#### 3.8 INTERIM ANALYSES

A non-binding interim futility analysis will be performed when approximately 50% of the primary endpoint events are observed. The futility criterion will be determined by calculating the predictive power, which is a weighted average of the conditional power (11). Futility of the study may be declared only when the predictive power for the primary endpoint is below 10%, which is equivalent to the condition that the hazard ratio between tolebrutinib and placebo derived from the primary analysis is greater than or equal to 0.92. The futility interim analysis will be conducted by an independent statistics group and reviewed by the DMC. Neither the Sponsor's team nor the Investigator's staff will have access to the treatment information at the individual participant level or group level before the study is formally unblinded after study completion or after the DMC recommendation and Sponsor agreement for stopping the trial. The details of the interim analysis will be included in the Data Monitoring Committee (DMC) SAP.

## 4 SAMPLE SIZE DETERMINATION

Approximately 1700 participants will be screened to achieve up to 1290 randomly assigned to study intervention (2:1 randomization ratio of tolebrutinib to placebo). This study is planned as an event-driven trial based on 6-month CDP. The study will continue until approximately 288 events are projected to have occurred to provide 80% power to detect a 30% risk reduction in 6-month CDP with tolebrutinib compared to placebo (2-sided  $\alpha = 0.05$ ). The following assumptions were used for the calculations: 2-year placebo event rate of 23.6%; annual discontinuation rate of 10%; constant hazard rates using a log-rank test; estimated enrollment period of 24 months with the last randomized participant followed for 24 months.

Actual recruitment and disability event rates may vary; therefore, it is possible to stop with a reduced sample size of around 1100 and still maintain study power by extending the duration of the trial, if needed, to reach approximately the same number of events. For example, it could be that the last randomized participant is followed for around 30 months instead of 24, if necessary. Additional recruitment of participants will not substantially reduce the trial duration. In any case, the power is based on the number of events, and the actual trial duration will be dependent on the observed placebo rate and treatment effect.

## 5 SUPPORTING DOCUMENTATION

#### 5.1 APPENDIX 1 LIST OF ABBREVIATIONS

9-HPT:	9-hole peg test
AE:	adverse event
AESIs:	adverse events of special interest
ALT:	alanine aminotransferase
ANCOVA:	analysis of covariance
AST:	aspartate aminotransferase
ATC:	anatomic therapeutic category
BVL:	brain volume loss
CDI:	confirmed disability improvement
CDP:	confirmed disability progression
CI(s):	confidence intervals
CMH:	Cochran-Mantel-Haenszel
C-SSRS:	Columbia Suicide Severity Rating Scale
CVLT-II:	California Verbal Learning Test-II
DB:	double-blind
DMC:	Data Monitoring Committee
ECG:	electrocardiogram
e-CRF:	electronic case report form
EDSS:	expanded disability status scale
EOS:	end of study
Gd:	Gadolinium
GLMM:	generalized linear mixed model
HLGT:	high-level group term
HLT:	high-level term
IMP:	investigational medicinal product
KM:	Kaplan-Meier
LLT:	lower-level term
LSM:	least squares means
MedDRA:	Medical Dictionary for Regulatory Activities
MMRM:	mixed-effect model with repeated measures
MRI:	magnetic resonance imaging
MS:	multiple sclerosis
MSFC-3:	multiple sclerosis functional composite
MSQoL-54:	multiple sclerosis quality of life-54
MTR:	magnetization transfer ratio
NCI-CTCAE:	National Cancer Institute Common Terminology for Adverse Events
NEDA-3:	no evidence of disease activity-3
NRSPMS:	non-relapsing secondary progressive multiple sclerosis
OL:	open-label
PCSA:	potentially clinically significant abnormality

PD:	pharmacodynamic
PK:	pharmacokinetics
PT:	preferred term
ROW:	rest of the world
RRMS:	relapsing-remitting multiple sclerosis
SDMT:	symbol digit modalities test
SE:	standard error
SOC:	system organ class
SPMS:	secondary progressive multiple sclerosis
T25-FW:	timed 25-foot walk
TE:	treatment-emergent
TEAE:	treatment-emergent adverse event
VAS:	visual analogue scale
WHO-DD:	World Health Organization-drug dictionary

#### 5.2 APPENDIX 2 PARTICIPANT DISPOSITIONS

The number (%) of participants included in each of the analysis populations listed in Table 3 will be summarized.

Screened subjects are those with a signed informed consent. Screen failures are defined as participants who consent to participate in the study but are not subsequently randomized. The number of screened participants will be summarized along with the number (%) of screen failures overall and by reason(s).

The number (%) of participants in the following categories will be provided:

- Exposed but not randomized, if applicable
- Randomized and not exposed, if applicable
- Randomized and exposed
  - Completed the DB study intervention period
  - Did not complete the DB study intervention period including main reason for discontinuation and reason for withdrawal by subject
  - Switched to the OL tolebrutinib treatment
  - Completed the OL period
  - Did not complete the OL period including main reason for discontinuation and reason for withdrawal by subject
- Completed the study
- Did not complete the study including main reason for study discontinuation
- Status at last contact (alive, dead)
- Entered LTS study

Reasons for permanent study intervention and study discontinuation, "adverse event" and "other reasons" will be split as related versus not related to COVID-19, if applicable.

For all categories of participants (except for nonrandomized) percentages will be calculated using the number of randomized participants as the denominator.

In addition, the number (%) of participants screened, screened-failed, randomized, with permanent study intervention discontinuation (DB and OL) and with early study discontinuation will be provided by country and site. Listings of other reasons for treatment discontinuation, and participants who are exposed but not randomized will be provided.

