For participants with definitive discontinuation of study drug who do not agree to remain in the study after the premature end of treatment visit, if the premature end of treatment visit is less than 3 weeks after the last dose of the study drug, an additional visit should be performed with assessments normally planned for the follow-up visit.

Participants who are treated with open label IMP who decide to prematurely and permanently discontinue the open label IMP prior to the common study end date should be assessed as soon as possible using the procedures normally planned for the premature end of treatment visit. Participants who prematurely and permanently discontinue open label IMP who do not agree to

remain in the study after performing a visit analogous to the premature end of treatment visit, should have an additional visit performed with assessments normally planned for the follow-up visit if the last study visit was less than 3 weeks after the last dose of the open label IMP.

Participants who prematurely and permanently end treatment for a reason other than 6-month CDP will not be eligible for open-label IMP.

All cases of definitive study drug discontinuation must be recorded by the Treating Investigator in the appropriate pages of the eCRF when considered as confirmed.

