9.4.5 Other safety analyses

All safety analyses will be performed on the safety population.

Safety summaries will be descriptive, ie, no statistical significance tests will be performed on safety data. The summary of safety results will be presented by treatment group.

Safety analyses will be based on the reported AEs and other safety information, such as clinical laboratory data, vital signs, and ECG.

The observation period will be divided into 4 epochs:

- The screening epoch is defined as the time from the signed informed consent date up to the first administration of the study intervention.
- The treatment epoch is defined as the time from the first administration of the study intervention to:
 - The earlier of last administration of the study intervention plus 10 days or first IMP in the LTS study for participants not receiving SAR442168 open-label treatment.
 - The first administration of SAR442168 open-label treatment for participants switching to open-label therapy.
- The open-label epoch, applicable only for participants switching to SAR442168 openlabel treatment, is defined as the time from first administration of SAR442168 open-label treatment to the earlier of last administration of open-label treatment plus 10 days or first IMP in the LTS study.
- If applicable, the post-treatment epoch is defined as the time from the end of treatment epoch (or end of open-label epoch, if applicable) to the participant's final study contact date.

The safety analysis of AEs will focus on TEAEs, defined as AEs that developed, worsened, or became serious during the treatment period. All AEs reported in this study will be coded using the Medical Dictionary for Regulatory Activities (MedDRA) version in effect at the time of database lock.

Endpoint	Statistical analysis methods
Adverse Events including AEs, TEAEs, SAEs, AEs leading to treatment discontinuation, AEs leading to death and AESIs	The number and percentage of participants with at least one TEAE, treatment-emergent SAE, TEAE leading to treatment discontinuation, TEAE leading to death, and treatment-emergent AESI will be tabulated by treatment group. Multiple occurrences of the same event in the same participant will be counted only once in the tables. The denominator for computation of percentages will be the safety population within each treatment group. Serious AEs and AEs leading to study discontinuation or death that occur outside the treatment-emergent period will be summarized separately.

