#### **Observation** period

The observation periods for safety will be divided into 4 epochs:

- The screening (pre-treatment) period is defined as the period from the signed informed consent date up to first administration of the study intervention.
- The **treatment period** (ie, treatment-emergent (TE) period) is defined as the period from the first administration of study intervention to
  - The earlier of last administration of the study intervention + 10 days or first IMP in the LTS study for participants not receiving tolebrutinib OL treatment,
  - The first administration of tolebrutinib OL treatment for participants switching to OL therapy

- The **OL period** (ie, OL TE period), applicable only for participants switching to tolebrutinib OL treatment, is defined as the time from first administration of tolebrutinib OL treatment to the earlier of last administration of OL treatment + 10 days or first IMP in the LTS study
- The **post-treatment period**, if applicable, is defined as the period from the end of treatment period (or end of OL period, if applicable) to the participant's final post-treatment study contact date.

Summaries of OL period data will be presented by original randomized treatment group and overall.

The on-study period is defined as the time from randomization until the end of the study defined as the last scheduled visit for those who completed the study and the end-of-study date collected on electronic case report form (e-CRF) page "Completion of End of Study" for those who did not complete the study. If death is the end-of-study reason, date of death will be used.

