#### 3.6 SAFETY ANALYSES

All safety analyses will be performed on the safety population as defined in Section 2, unless otherwise specified, using the following common rules:

- The analysis of the safety variables will be descriptive with no testing planned. The summary of safety results will be presented by treatment group.
- Safety data in participants who do not belong to the safety population (eg, exposed but not randomized) will be provided separately.

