#### Analysis of all adverse events

The overview of TEAE will be generated presenting the number (%) of participants with:

- Any TEAE
- Any treatment emergent SAE
- TEAE leading to death
- Any TEAE leading to permanent study intervention discontinuation
- Any treatment emergent AESI
- Any TEAE considered by the investigator as related to study intervention

Similar summaries for OL emergent AEs will also be provided. An additional overview summary including the number and rate of events will be provided in the DB treatment period and OL period respectively.

The AE summaries of Table 5 will be generated with number (%) of participants experiencing at least one event.

Listings of SAEs from randomized participants, AEs from participants who are treated but not randomized, AEs leading to treatment discontinuation and severe AEs will be provided.

Type of AE	MedDRA levels
AII TEAE	Primary SOC and PT
	PT (incidence ≥2%)
Severe (grade ≥3) TEAEs	Primary SOC and PT
	PT
TEAE related to IMP as per Investigator's judgment	Primary SOC and PT
	PT
Treatment emergent SAE	Primary SOC and PT
	PT

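### Open-label completion and discontinuation are to be shown as percentages of all randomized participants, although only those who switch after 6-month CDP can have these outcomes; for open-label adverse events no denominator is stated

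*SAP*

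**What the plan says.** SAP 5.2 (Appendix 2) asks for number and percentage in a list of categories. Three concern the OL period: participants who switched to OL tolebrutinib, those who completed the OL period, and "Did not complete the OL period including main reason for discontinuation and reason for withdrawal by subject". One rule then covers the whole list: "For all categories of participants (except for nonrandomized) percentages will be calculated using the number of randomized participants as the denominator". The OL rows have no exception.

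Entry to OL is restricted. Protocol 6.6.1 offers it to participants who reach 6-month CDP, and Protocol 7.1.1 adds: "Participants who prematurely and permanently end treatment for a reason other than 6-month CDP will not be eligible for open-label IMP". The switch is optional. Protocol 6.6.1 lets a participant stay on double-blind treatment after CDP and bars a switch when certain liver or alcohol criteria are met. Neither document gives an expected uptake.

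For safety, SAP 3.6 sets a default: "All safety analyses will be performed on the safety population as defined in Section 2, unless otherwise specified". The populations table in SAP section 2 contains no OL-treated set. After the overview of treatment-emergent events, SAP 3.6.2 adds: "Similar summaries for OL emergent AEs will also be provided". Protocol 9.4.5, Table 4, in a row written for treatment-emergent events, says: "The denominator for computation of percentages will be the safety population within each treatment group". SAP 3.1 sets the columns: "Summaries of OL period data will be presented by original randomized treatment group and overall".

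**The concern.** The number randomized is the right base for the proportion who switched. It is the wrong base for what happened to those who switched: everyone who never took an OL dose enters the denominator as if they could have stopped OL treatment. The printed percentage is then the true percentage multiplied by the proportion of the arm that switched. That proportion is small, and it differs between arms whenever the drug delays progression.

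Within this study, OL treatment is the only first exposure to tolebrutinib for participants randomized to placebo. Protocol 2.3 names drug-induced liver injury as an identified risk, with cases in Months 1 to 3, and Protocol 6.6.1 restarts frequent liver testing after the first OL dose. The additional liver-injury analyses in SAP 3.6.3.1 are largely framed on the treatment-emergent period, which SAP 3.1 ends at the first OL dose for switchers. OL disposition and incidence tables will therefore be read closely, side by side by randomized arm.

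**Working it through.** **Inputs** (Protocol 9.2 and SAP section 4): 2-year placebo event rate 23.6%; hazard ratio 0.70; annual discontinuation 10%; constant hazards; 24 months of enrollment plus 24 months of follow-up for the last participant; 2:1 allocation; up to 1290 participants, or about 1100 with about 30 months of minimum follow-up; 288 events. Uptake of the OL switch is not given, so I assume 60-100%.

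**1. The plan's own figure.** Schoenfeld power with 288 events at 2:1: √(288 × 1/3 × 2/3) × |ln 0.70| − 1.96 = 8.00 × 0.3567 − 1.96 = 0.893, which gives 81.4% power against the stated 80%. The same formula needs 278 events for exactly 80%, so 288 is slightly conservative. The design inputs are consistent.

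**2. Share of each arm with an event.** Monthly hazards: placebo λ = −ln(0.764)/24 = 0.01122; tolebrutinib 0.70 × λ = 0.00785; dropout δ = −ln(0.90)/12 = 0.00878. Share = λ/(λ+δ) × [1 − mean of exp(−(λ+δ)f)], with follow-up f uniform on 24 to 48 months.
- Placebo: 0.561 × (1 − 0.491) = 28.5%.
- Tolebrutinib: 0.472 × (1 − 0.553) = 21.1%.
- With 1290 participants this gives 430 × 0.285 + 860 × 0.211 ≈ 304 events, close to the planned 288.

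**3. Share that can switch.** The onset must fall at least 6 months before study end, so f runs from 18 to 42 months.
- Placebo: 0.561 × (1 − 0.554) = 25.0%.
- Tolebrutinib: 0.472 × (1 − 0.611) = 18.4%.

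A simulation that also requires the participant to stay in the study for the 168-day confirmation gives 24.1% and 17.7%. With 28-day months it gives 22.4% and 16.4%.

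**4. Dilution at full uptake** = 1 / share switching.
- Placebo: 1/0.250 = 4.0. Tolebrutinib: 1/0.184 = 5.4 to 5.5. From the simulated shares: 4.1 and 5.6.
- Illustration with an assumed true OL discontinuation rate of 20% in both arms: 0.20 × 25.0% = 5.0% printed for placebo and 0.20 × 18.4% = 3.7% for tolebrutinib.

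**5. Range over uptake and sample size.** Fix the total at 288 events, take the tolebrutinib share as 0.74 of the placebo share (21.1/28.5), and treat every event as a possible switch. The placebo share is then 288 / [N × (1 + 2 × 0.74)/3].

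| N | Uptake | Placebo fold | Tolebrutinib fold | Overall fold |
|---|---|---|---|---|
| 1290 | 100% | 3.7 | 5.0 | 4.5 |
| 1290 | 80% | 4.6 | 6.3 | 5.6 |
| 1290 | 60% | 6.2 | 8.3 | 7.5 |
| 1100 | 100% | 3.2 | 4.3 | 3.8 |
| 1100 | 80% | 4.0 | 5.3 | 4.8 |
| 1100 | 60% | 5.3 | 7.1 | 6.4 |

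**6. Difference between columns.** With equal uptake, the ratio of printed percentages at identical true risk equals the ratio of shares: 28.5/21.1 = 1.35 (25.0/18.4 = 1.36). At a hazard ratio of 1 the shares are equal and the ratio is 1, but the dilution remains: 1290/288 = 4.5-fold in both arms.

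**7. Which tables are touched.** The disposition rule is explicit. For OL adverse events, AESIs, PCSA and C-SSRS, the only candidate denominators are the SAP 3.6 default and the Table 4 sentence, and neither mentions OL. Continuous OL laboratory, vital sign and ECG summaries use available observations (SAP 3.1 and 3.6.3.1). OL exposure duration needs a first and last dose and its categories start above zero (SAP 3.6.1). Non-switchers contribute nothing to these, so there is no dilution.

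**The case against.** The strongest reply is that nothing is hidden. The count of switchers stands just above the OL completion rows, so the conditional percentage is one division away. A figure labelled as a percentage of those randomized is not false. SAP 3.6.1 plans OL exposure, and SAP 3.6.2 adds: "An additional overview summary including the number and rate of events will be provided in the DB treatment period and OL period respectively". SAP 3.6 calls the safety analysis descriptive with no testing, and SAP 3.6.2 puts its focus on double-blind events. All of this stands, and it is why the point concerns reporting only.

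A reader might also infer that the plan commits OL adverse event rates to the same several-fold understatement. The documents do not support that as a stated rule. The Table 4 sentence is written for treatment-emergent events, and that epoch closes for switchers at the first OL dose. SAP 3.6 allows exceptions. SAP 3.1 says the OL period applies only to switchers. The request for similar summaries fixes content, not a denominator. What remains is that the SAP names no OL denominator, and a programmer who applies the default would produce the dilution.

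The size is conditional too: 4- to 5.5-fold is the full-uptake planning case, not a bound.

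**Conclusion.** The point holds for disposition. SAP 5.2 sets an explicit denominator that does not fit OL completion and discontinuation. OL discontinuation percentages would be understated about 4-fold (placebo) and 5.5-fold (tolebrutinib) under the planning assumptions with full uptake, and roughly 3- to 8-fold by arm over an assumed 60-100% uptake and 1100-1290 participants. The former-placebo column would look about 1.35 times higher at equal true risk if the hazard ratio is 0.70 and uptake is equal; this does not occur at a hazard ratio of 1. For OL adverse event, AESI, PCSA and C-SSRS incidence, the finding is an unstated denominator whose default would have the same effect. It would be wrong to extend the point to continuous or exposure-duration summaries, or to any primary, secondary or futility result. It should be corrected, because it bears on how first tolebrutinib exposure in former placebo participants is read.

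**What to change.** - In SAP section 2, define an OL-treated set: participants with at least one OL tolebrutinib dose, shown by randomized arm and overall. Naming the randomized arm also avoids confusion with the as-treated rule there, which assigns anyone given more than one intervention to tolebrutinib.
- In SAP 5.2, use this set as the denominator for OL completion and for OL non-completion with reasons. Keep the number randomized for the row that counts switchers.
- In SAP 3.6, use it for OL adverse event, AESI, PCSA and C-SSRS percentages, and state that the Protocol Table 4 denominator applies to the double-blind period.
- Leave the continuous OL laboratory, vital sign and ECG summaries and the OL exposure-duration summaries as they are.

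The cost is one population flag and a few sentences of SAP text. No new data are needed.

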#### Protocol deviations

Critical and major protocol deviations (automatic or manual) will be summarized in the randomized population as well as displayed separately as related versus not related to COVID-19 if applicable. A listing of critical and major protocol deviations will be provided.

## 5.3 APPENDIX 3 DEMOGRAPHICS AND BASELINE CHARACTERISTICS, PRIOR OR CONCOMITANT MEDICATIONS

#### Demographics, baseline characteristics, medical surgical history

The following demographics and baseline characteristics, smoking and alcohol history, disease characteristics at baseline, and medical and surgical history will be summarized using descriptive statistics in the randomized population.

Demographic and baseline characteristics

- Age in years as quantitative variable and in categories ( $\leq 40$ , >40; 18 to 60)
- Sex (Male, Female)
- Race (White, Black or African American, Asian, American Indian or Alaska Native, Native Hawaiian or Other Pacific Islander, Multiple, Unknown, Not reported)
- Ethnicity (Hispanic or Latino, not Hispanic or Latino, Unknown, Not reported)
- Region (US, non-US; North America, Western Europe, Eastern Europe, ROW)
- Weight in kg as a quantitative variable
- BMI in kg/m^2 as a quantitative variable and in categories (<25,  $\geq 25$  to <30,  $\geq 30$ )

Smoking and alcohol habits

- Smoking history (Never, Current, Former)
- Cessation prior to screening for Former smokers in months
- Cigarettes per day for smokers

- Frequency of alcohol drinking in the past 12 months (Never, Occasional, At least monthly, At least weekly, At least daily)
- # Standard alcohol drinks on typical day when drinking (1 or 2, >2)

Disease characteristics at baseline

- Time since symptom onset of relapsing-remitting multiple sclerosis (RRMS) in years
- Time since diagnosis of secondary progressive multiple sclerosis (SPMS) in years
- Time since most recent relapse in years
- Baseline EDSS score as a quantitative variable (average of screening and baseline scores when both available)
- Disease burden at baseline (baseline EDSS  $\leq$ 4.5 versus >4.5; EDSS  $\leq$ 5.5 versus >5.5)
- Baseline Gd-enhancing T1 lesion (absent, present)

Baseline safety and efficacy parameters (apart from those listed above) will be presented along with the safety and efficacy summaries.

Relevant medical (or surgical) history collected in the eCRF will be coded to a LLT, PT, HLT, HLGT, and associated primary SOC using the MedDRA version currently in effect at Sanofi at the time of database lock and will be summarized by primary SOC and HLT (internationally agreed SOC order and decreasing frequency of HLTs in the Overall group).

